### 25.4 Secondary outcome analyses

Quantitative variables were compared with Student's unpaired t-test, paired t-test, Wilcoxon rank sum test (Mann-Whitney  $U$  test), or generalized linear mixed models (GLMM). GLMMs were employed to compare the difference between the two groups in HAS changes from baseline to 6 months. Categorical variables were analyzed with Fisher's exact test or a chi-square test, and 95% confidence intervals were calculated. Kaplan-Meier curves were used to visualize the time to treatment discontinuation.

All secondary outcomes were analyzed based on the intention-to-treat principle without imputation of missing values.

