## 12 Sample size determination

In this trial, propranolol was used as the control group to evaluate the efficacy and safety of the atenolol group (experimental group). The treatment response after 6 months of medication was used as the key therapeutic index. To calculate the sample size for this trial, we used the following assumptions:

- (1) A 2-sided 0.05 significance level;
- (2) Ratio of the propranolol group: atenolol group = 1:1;
- (3) A statistical power of 90%;
- (4) A 20% dropout rate due to ineligibility;
- (5) A follow-up of at least 96 weeks;
- (6) A 24-month recruitment period; and
- (7) In this trial, the atenolol group's evaluation variables were compared with the propranolol group's evaluation variables to test for noninferiority. The hypotheses are listed below:

-H0: Twenty-four weeks after therapy initiation, compared to the treatment response of propranolol therapy, that of atenolol was inferior; and

-H1: Twenty-four weeks after therapy initiation, compared to the treatment response of propranolol therapy, that of atenolol was non-inferior.

(8) Very limited data are available in the literature that can be used to set hypotheses for atenolol treatment. Existing case studies are mainly based on small single-center experiences. According to previous studies, propranolol's total treatment response is assumed to be 70-100%, and atenolol's total treatment response is assumed to be 70-100%. In addition, assuming that the atenolol on propranolol response rate does not fall by greater than 15%, the noninferiority margin was selected to be -15%.

(9) Assuming the ulceration rate in both groups to be 10%.

(10) A sample size of 180 patients was determined to be required for each group (a total of 360 patients).

[figure not shown]
[figure not shown]
---

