#### ***20.4 Complete healing time of ulceration***

Additional information was collected by site investigators for patients with ulceration. Ulceration is defined as a break in the integrity of the hemangioma surface epithelium (or skin) with or without infection. The information included the extent of ulceration, complications of ulceration, prior duration of ulceration (before treatment), concurrent treatments, and complete healing time. Prior duration of ulceration was defined as the time from the first sign of ulceration until before  $\beta$ -blocker treatment. The complete healing time of the ulceration was defined as the time from the first dosage of propranolol or atenolol until complete healing of the hemangioma ulceration. Concurrent treatments, including oral pain medication, oral antibiotics, topical ointment antibiotics and/or wound dressings, were permitted to treat ulcerated IH and were recorded.

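### Ulcer healing time is a time-to-event secondary outcome, but the plan gives it no censored-data method, observation window or rule for ulcers that have not healed

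*Combined protocol and SAP*

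**What the plan says.** Section 20.4 makes healing time a duration that ends in an event: "The complete healing time of the ulceration was defined as the time from the first dosage of propranolol or atenolol until complete healing". It gives no end of observation, no censoring rule, and no value for an ulcer that never heals or an infant who leaves first.

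Section 25.4 names no method for this outcome. Its general rule reads "Quantitative variables were compared with Student's unpaired t-test, paired t-test, Wilcoxon rank sum test", with generalized linear mixed models as a further option. The one use stated for those models is the Hemangioma Activity Score: "GLMMs were employed to compare the difference between the two groups in HAS changes from baseline to 6 months". Kaplan-Meier appears once, for a different variable and only as a display: "Kaplan-Meier curves were used to visualize the time to treatment discontinuation". No log-rank test or Cox model is named anywhere.

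On incomplete data, Section 25.4 says: "All secondary outcomes were analyzed based on the intention-to-treat principle without imputation of missing values". Section 24 discusses missing data in general terms, does not mention censoring, and ties its sensitivity analysis to the week-24 primary outcome.

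**The concern.** An infant whose ulcer is still open has no healing time, only a lower bound for it. A t-test or Wilcoxon test on observed values cannot use that bound, and without imputation the infant contributes nothing. What remains is a comparison among infants who healed.

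That comparison is selected on the outcome. If one drug heals more slowly, more of its long times go unobserved, so its average is shortened more and the difference shrinks. In the extreme, a drug that leaves many ulcers unhealed could look equal to one that heals nearly all of them.

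Such exits are foreseeable. Section 19 provides for withdrawal from treatment for nonresponse or severe adverse events, Section 21.8 lists events that mandate termination, and Section 12 allows for 20% dropout. Withdrawal for nonresponse is plausibly linked to slow healing.

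**Working it through.** **Inputs from the plan (Section 12).** 180 infants per group; "Assuming the ulceration rate in both groups to be 10" (per cent); "A 2-sided 0.05 significance level"; 90% power; margin 15 percentage points; 20% dropout; follow-up of at least 96 weeks. The plan gives no healing medians, so those below are assumptions.

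**The plan's own figure.** With a common response rate p, n = (1.960 + 1.282)² × 2p(1 − p) / 0.15². The plan gives p only as 70–100%. At an assumed p = 0.81, n = 10.51 × 0.3078 / 0.0225 ≈ 144, and 144 / 0.8 = 180. The 180 is not in dispute. It implies 180 × 0.10 = 18 ulcerated infants per arm, 36 in all.

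**Healed-only mean under exponential healing.** For median m and observation to week T:

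- mean over all ulcers: μ = m / ln 2
- proportion unhealed at T: S = 2^(−T/m)
- mean among the healed: μ − T·S / (1 − S)

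**Medians 6 and 9 weeks, T = 24.**

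- Faster arm: μ = 8.66; S = 0.0625; healed-only mean = 8.66 − 24 × 0.0625 / 0.9375 = 7.06.
- Slower arm: μ = 12.98; S = 0.157; healed-only mean = 12.98 − 24 × 0.157 / 0.843 = 8.50 (unrounded S).
- The mean gap falls from 4.33 to 1.44 weeks. Healed-only medians are 5.48 and 7.10, so the median gap falls from 3.0 to 1.6 weeks.
- Infants lost: 18 × 0.0625 ≈ 1 and 18 × 0.157 ≈ 3.

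**Same medians, T = 96, no dropout.** S = 2^(−16) ≈ 0.002% and 2^(−10.67) ≈ 0.06%. Healed-only means are about 8.65 and 12.92, a gap of 4.27 weeks, or about 1% shrinkage.

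**Range over assumed medians (mean gap in weeks, no dropout).**

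| Medians | True gap | Healed-only, week 24 | Shrinkage | Healed-only, week 96 | Shrinkage |
|---|---|---|---|---|---|
| 4 v 6 | 2.89 | 1.67 | 42% | 2.88 | 0% |
| 4 v 8 | 5.77 | 2.72 | 53% | 5.75 | 0% |
| 6 v 9 | 4.33 | 1.44 | 67% | 4.27 | 1% |
| 6 v 12 | 8.66 | 2.26 | 74% | 8.28 | 4% |
| 8 v 16 | 11.54 | 1.84 | 84% | 10.04 | 13% |

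**Simulated power, 18 per arm, 1,500 trials per scenario.**

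- 4 v 8 weeks to week 24: healed-only Wilcoxon 0.25, log-rank with censoring 0.51.
- 8 v 16 to week 24: 0.09 against 0.43. To week 96: 0.39 against 0.52.
- Adding 20% dropout to 8 v 16 at week 96 lowers the simulated healed-only gap from 10.2 to 9.3 weeks (true gap 11.5).
- If healers heal equally fast (median 4 weeks) but 95% against 50% ever heal, the healed-only Wilcoxon test rejects in 5% of trials to week 24 and the log-rank test in 82%.

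**Ceiling on power.** By Schoenfeld's formula with all 36 ulcers healing, power is Φ(√36 / 2 × ln 2 − 1.96) = 0.55 at a hazard ratio of 2, and 0.23 at 1.5.

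**The case against.** The strongest reply is that the plan is silent rather than wrong. Nowhere does it say that healing time goes to a t-test or Wilcoxon test, or that unhealed infants are dropped. Both are inferences. Section 25.4 invokes intention to treat, which pulls against dropping them, and a log-rank analysis also imputes nothing. This stands as a limit on wording. It does not remove the gap: no method listed for quantitative variables handles censoring as described, and the survival method that the authors had to hand is given to another variable.

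Second, a reader might take the week-24 result as the size of the bias. Section 20.4 sets no such cut-off, and Sections 9, 12 and 21.8 put follow-up at 96 weeks. Over that window without dropout the shrinkage is small. This stands, and the size must be given as a range.

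Third, a reader might infer that the bias runs in the unsafe direction for a noninferiority claim. The documents do not support that. The −15% margin and the hypotheses in Section 12 concern only week-24 treatment response; healing time has no margin. The bias favours the slower drug, and the documents do not say which that is. If propranolol were slower, atenolol's advantage would be understated. Clearly unequal withdrawal could change the direction.

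Fourth, treatment failure in Section 19 means leaving trial treatment, not follow-up, so a healing time could still be recorded afterwards. This stands too: such infants need not be lost.

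**Conclusion.** The concern holds as a gap in the analysis of one secondary outcome. Followed as written, Section 25.4 leaves unhealed ulcers without a value and outside the comparison, which dilutes a true difference provided that loss is similar in the two arms.

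Under assumed exponential healing, the dilution of the mean gap is 42–84% with observation to week 24 and 0–13% with observation to week 96 and no dropout. Which applies cannot be settled from the documents, because the window is unstated, and that omission is part of the defect. Withdrawal before healing would add to the bias. About 18 infants per arm are concerned. The primary noninferiority conclusion is untouched, and power for this outcome is low under any method.

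**What to change.** Amend Section 25.4, with a matching line in Section 20.4:

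- **Population and time zero:** all randomised and dosed infants with ulceration at baseline, timed from first dose. Undosed infants have no time zero.
- **Window:** state when observation of healing ends, and count healing recorded after treatment stops where available.
- **Censoring:** censor unhealed ulcers at the last assessment.
- **Report:** Kaplan-Meier estimates by arm, a log-rank test, a hazard ratio with 95% CI, and the number unhealed per arm.
- **Sensitivity analysis:** treat infants withdrawn for nonresponse as unhealed to the end of the window, because censoring them at withdrawal assumes that leaving says nothing about healing.

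The cost is SAP wording and a small amount of extra analysis. One check is needed: Section 20.4 has sites record healing time but does not mention dated ulcer assessments for infants who stay unhealed, so the last-assessment date may have to come from visit records. The change does not cure the low power, so the estimate and its interval should carry the interpretation rather than the P value.

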## **9 Expected duration**

Research duration: 4 years.

Recruitment period: 2 years.

After enrolment, each study subject was followed up for 96 weeks following the start of study treatment.

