### ***17.3 Other co-interventions***

In both arms, oral antibiotics (cefaclor suspension), topical ointment antibiotics (mupirocin) and/or wound dressings were permitted to treat ulcerated IH and were recorded. The requirement for any additional IH-specific intervention was considered treatment failure.

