## 19 Primary outcome measures

The primary outcome measure was the clinical response at 6 months in the intention-to-treat population. The intention-to-treat population was defined as all patients who had undergone randomization. If after assignment, a patient did not receive a drug administration or if an evaluation was never made after drug administration, the patient was excluded from the intention-to-treat population.

Digital photographs of IHs were independently obtained by three investigators who were unknown to the study group assignment. In the case of multiple IHs, only the most clinically important IH (typically the largest or most ulcerated IH) was documented.

Changes in IH size and color were classified as a complete response, nearly complete response, partial response or no response. The primary outcome measure was any response or nonresponse at 6 months in the intention-to-treat population of all patients who underwent randomization. The any response included compete, nearly complete and good responses; the nonresponse included stable or deteriorated:

-A complete response was defined as no redundant tissue or telangiectasia was identified.

-A nearly complete response was defined as a minimal degree of telangiectasis, erythema and skin thickening.

-A partial response was defined as a size reduction or change in color that did not meet the nearly complete resolution criteria.

-Stable was defined as no changes in size or color between baseline and month 6.

-Deterioration was defined as further growth of the target hemangioma.

Treatment failure was defined as patients withdrawing from trial treatment due to nonresponse and/or severe adverse events.

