### ***20.6 Responses at Week 96***

A complete/nearly complete response at week 96 was considered median-term efficacy. The digital photographs of the target hemangioma were assessed by centralized evaluation at West China Hospital of Sichuan University. Three trained investigators who were unknown of the study-group assignments independently evaluated the digital photographs taken at baseline and week 96 after the initial treatment. For more details regarding the procedures for median-term efficacy, refer to the **Collection and Assessment of Series Digital Photographs** section.

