## ***21.8 Termination of the study***

All participants were informed that they had the right to withdraw from the study at any time without prejudice to their medical care and that they were not obliged to state their reasons. Follow-up was considered complete when the participant completed all study procedures and assessments up to the 96-week visit. Termination of the study was mandatory in the following situations:

- Any grade  $\geq 4$  adverse event;
- Recurrent or persistent cases of hypoglycemia, bronchitis with dyspnea, bronchial hyperreactivity or bronchospasms.
- Persistent hypotension; or

---

-Persistent bradycardia.

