### 25.3 Primary outcome analysis

Based on the intention-to-treat principle, the primary outcome analysis was performed in the intention-to-treat population. All patients treated with at least one dose of study medication (propranolol or atenolol) were included and analyzed in the group to which they were randomized.

Primary outcomes were analyzed by sensitivity analysis. Best-case (response) and worse-case (nonresponse) scenarios were evaluated based on the intention-to-treat principle (in the best-case scenario, missing data in the propranolol group were considered failures, and missing data in the atenolol group were considered successes). In addition, missing data in the propranolol group were considered successes, and missing data in the atenolol group were considered failures.

In addition, a per protocol analysis was performed. This means that only patients without major protocol violations are included. These patients fulfilled all inclusion and exclusion criteria and carried out all medical procedures/visits according to the protocol.

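### Week-96 response is called intention-to-treat, but with no imputation it is in effect an observed-case rate, and no planned sensitivity analysis covers it

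*Combined protocol and SAP*

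**What the plan says.** Section 25.4 sets one rule for every secondary outcome: "All secondary outcomes were analyzed based on the intention-to-treat principle without imputation of missing values". Categorical outcomes are compared by Fisher's exact or chi-square test with 95% confidence intervals. The mixed model is committed to only for the Hemangioma Activity Score (HAS) up to month 6.

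The week-96 outcome is defined in Section 20.6: "A complete/nearly complete response at week 96 was considered median-term efficacy". Blinded central assessors read it from the baseline and week-96 photographs. Section 18 schedules photographs at baseline and weeks 1, 4, 12, 24 and 96, so no scheduled image falls between weeks 24 and 96.

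Three provisions bear on who might lack the last photograph or how they would be scored:

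- Section 19: "Treatment failure was defined as patients withdrawing from trial treatment due to nonresponse and/or severe adverse events".
- Section 17.3: "The requirement for any additional IH-specific intervention was considered treatment failure".
- Section 21.8: "Termination of the study was mandatory in the following situations", followed by a list of toxicities.

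None says how such an infant counts at week 96.

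The missing-data provisions lie elsewhere. Section 25.3 gives best- and worst-case scenarios for the primary outcome; in one of them "missing data in the propranolol group were considered failures, and missing data in the atenolol group were considered successes". Section 24 says that missing data were analysed in several ways, but ties its sensitivity analysis to the week-24 primary value.

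**The concern.** A 2x2 table needs a yes or a no from each infant. If no value may be imputed and no scoring rule exists, an infant without the week-96 photograph drops out of numerator and denominator alike. What is then reported under an intention-to-treat label is the rate among infants who were photographed. Section 24's other remedy, a covariance structure, suits repeated measures and not a single-visit binary outcome.

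There are reasons to think that loss could be informative. The trial is open-label, follow-up lasts 96 weeks, and study termination is mandatory for listed toxicities. Section 5 expects the two drugs to differ in adverse effects, so exits could be unequal between arms. At stake is the outcome that the plan presents as its median-term efficacy. A reader would have no pre-planned analysis showing how far, or which way, missing photographs had moved it.

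**Working it through.** **1. The plan's own figures.** The documents give no week-96 response rate, no week-96 loss and no split of loss by arm. Section 12's 70-100% is total treatment response for the week-24 comparison, and its 20% dropout is attributed to ineligibility. The nearest stated figure is 180 per group. It reproduces if 80% response in both arms is inferred from the range (one-sided 0.025, 90% power, 15-point margin):

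n = (1.960 + 1.282)² x 2 x 0.80 x 0.20 / 0.15² = 10.51 x 0.32 / 0.0225 = 149.5, so 150; and 150 x 1.2 = 180.

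The match is conditional on the inferred 80%, and dividing 150 by 0.8 would give 188. The figure serves below only as a denominator.

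**2. Formula.** In one arm let R be the true rate among all infants in the analysis set, d the fraction without a week-96 photograph, and q the response rate among those infants. The observed-case rate is

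c = (R - d x q) / (1 - d), so its bias is c - R = d x (R - q) / (1 - d).

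The bias is upward if the missing infants respond less often than the arm as a whole (q < R), zero if q = R, and downward if q > R.

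**3. Numbers.** Assumed: R = 70% in both arms, so the true difference is 0; d = 20% on propranolol and 10% on atenolol; q the same in both arms.

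| q | Propranolol c | Atenolol c | Atenolol minus propranolol |
|---|---|---|---|
| 0% | 0.70/0.80 = 87.5% | 0.70/0.90 = 77.8% | -9.7 |
| 35% | 0.63/0.80 = 78.75% | 0.665/0.90 = 73.9% | -4.9 |
| 70% | 0.56/0.80 = 70.0% | 0.63/0.90 = 70.0% | 0 |
| 100% | 0.50/0.80 = 62.5% | 0.60/0.90 = 66.7% | +4.2 |

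Swapping the two loss rates reverses every sign. With R = 80% and the same losses, the differences are -11.1 (q = 0), -5.6 (q = 40%), 0 (q = 80%) and +2.8 (q = 100%).

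**4. The first row as counts.** Take 180 per arm, 126 responders in each, and 36 and 18 missing. Observed rates are 126/144 and 126/162. The standard error is the square root of (0.875 x 0.125/144 + 0.778 x 0.222/162) = 0.0427. The 95% interval is -9.7 ± 1.96 x 4.27, or -18.1 to -1.3 points. It excludes zero although the true difference is zero. Section 25.3's style of bounds on the same data would run from (126 - 162)/180 = -20 points to (144 - 126)/180 = +10 points, which shows the uncertainty openly.

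**5. Equal loss.** With 20% lost in both arms and q = 0, both rates read 87.5%, which is 17.5 points too high, but the difference stays at 0.

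**The case against.** The strongest reply is that the documents do not say who is missing. A reader might infer that the missing infants are mostly failures, that both reported rates are therefore too high, and that the arm losing more infants is always flattered. The text does not support these steps.

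- Section 19 speaks of withdrawal from trial treatment, not from follow-up. Section 9 says that "each study subject was followed up for 96 weeks following the start of study treatment", and Section 21.8 counts follow-up as complete only at the week-96 visit. A nonresponder who stops treatment may still be photographed. Only the toxicity list in Section 21.8 points to leaving the study, and an infant who leaves for toxicity need not be a nonresponder.
- Under Section 22, treatment is tapered and stopped on complete or nearly complete resolution after month 6. Some infants who miss week 96 may be resolved ones, and then the bias reverses.

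Three further replies have weight. The observed-case denominator is inferred, not written, and Section 24's several ways of handling missing data could be read as wider. Differential loss would not go unseen, because Section 25.5 lists discontinuations by arm, time and reason, and Section 25.4 plots time to treatment discontinuation. And this is not the key secondary outcome: HAS is, and a likelihood-based mixed model uses all observed visits and is valid under missing at random without imputation. Nor does the point call for a change to quality of life, which has a single post-baseline visit (week 48), so a likelihood model would add little there.

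These replies settle the direction and limit the scope. They do not close the gap: a listing shows loss but does not correct for it, and Section 24 names no analysis for week 96.

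**Conclusion.** The point holds for week-96 response, in conditional form. Section 25.4 states a rule that, on its natural reading, yields an observed-case rate under an intention-to-treat label, and the plan's bounding and sensitivity analyses stop at the week-24 primary outcome. This is a weaker stated method, not merely missing detail.

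The size cannot be derived from the documents. Under the assumed 70% true rate and 20% versus 10% loss, the spurious difference lies between -9.7 and +4.2 points, depending on how the missing infants fared, and is zero if loss is unrelated to outcome. It also depends on the gap in loss between arms: equal loss with equal true rates and equal response among the missing shifts the levels but not the difference. The documents do not establish which way the bias runs. The change is a cheap improvement to a non-key secondary outcome and does not touch the primary conclusion.

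**What to change.** In Section 25.4, replace the sentence for week-96 response with the following:

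1. **Set and data.** Analyse the full intention-to-treat set and state the denominator. Use any available week-96 photograph, whether or not treatment had stopped. Section 19 already narrows this set (for an infant never dosed or never evaluated, "the patient was excluded from the intention-to-treat population"), so it is not the same as all randomised infants.
2. **Main analysis.** Multiply impute missing week-96 responses from arm, week-24 response, HAS and reason for discontinuation.
3. **Bounds.** Extend the two extreme-case scenarios of Section 25.3 to week 96.
4. **Sensitivity analyses.** Report the complete-case result, and a result counting treatment failures as nonresponders. The latter should not be the main analysis: it is a composite outcome that could override a photograph showing resolution.
5. **Reporting.** Give the number of missing week-96 photographs by arm and reason.
6. **Consistency.** Reconcile the several analyses promised in Section 24 with the no-imputation rule in Section 25.4.

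The cost is SAP wording and a little more analysis. No new data are needed, since the imputation variables are already collected. Week-96 rates may come out lower and less precise than the complete-case figures.
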